#### 1.1.2. PCSK9 Biology and Target Rationale

PCSK9 is a member of the subtilisin serine protease family. Proprotein convertase subtilisin kexin type 9 is predominantly expressed by the liver and is critical for the down regulation of hepatocyte low-density lipoprotein receptor (LDLR) expression [Mousavi et al, 2009]. LDL-C levels in plasma are markedly elevated in humans with gain of function mutations in PCSK9, classifying them as having severe familial hypercholesterolemia [Abifadel et al., 2003]. Data from genetic association studies have identified loss of function alleles in human PCSK9 that result in lower PCSK9 protein levels and lower LDL-C levels [Zhao et al, 2006; Hooper et al, 2007; Horton et al, 2009]. In one published study, heterozygous individuals (carrying a single copy of a loss of function PCSK9 mutation) had significantly lower LDL-C with median levels of approximately 70 mg/dL (1.81 mmol/L) [Cohen et al, 2006]. Over a 15-year period of retrospective data analysis, this sustained lowering in LDL-C levels translated to an 88% lower risk of risk for CHD. Follow-up publications describe two adult individuals that are compound heterozygous for loss of function alleles of PCSK9. These individuals lack detectable plasma PCSK9 protein, have LDL-C levels <20 mg/dL, and yet are otherwise healthy [Zhao et al, 2006; Hooper et al, 2007]. Additionally, recent human clinical trials with PCSK9 blocking antibodies have shown significant lowering of LDL-C in healthy volunteers and across a range of high cardiovascular (CV)-risk populations and with elevated LDL-C both with and without statins [Banerjee et al, 2012; Dias et al, 2012; Milazzo et al, 2012; Raal et al, 2012; Roth et al, 2012; Stein et al, 2012; Sullivan et al, 2012; Hooper et al, 2013]. Two monoclonal agents to inhibit PCSK9 are currently approved in Europe and North America. Recent cardiovascular outcomes trials have further confirmed that PCSK9 is a validated drug target whose inhibition results in LDL-C lowering and

significant outcomes benefit without otherwise negatively impacting overall health [Ridker et al, 2017; Sabatine et al, 2017].

#### 1.1.3. Mechanism of RNA Interference

Ribonucleic acid interference (RNAi) is a naturally occurring cellular mechanism for regulating gene expression that is mediated by small interfering RNAs (siRNAs). Typically, synthetic siRNAs are 19-base to 25-base pair double-stranded oligonucleotides in a staggered duplex with a two- to four-nucleotide overhang at one or both of the 3' ends. Such siRNAs can be designed to target an endogenous messenger RNA (mRNA) transcript of a given gene. When introduced into cells, the guide (or antisense) strand of the siRNA loads into an enzyme complex called the RNA-Induced Silencing Complex. This enzyme complex subsequently binds to its complementary mRNA sequence, mediating cleavage of the target mRNA and the suppression of the target protein encoded by the mRNA [Elbashir et al, 2001].

Since unmodified siRNAs are rapidly eliminated and do not achieve significant tissue distribution upon systemic administration [Soutschek et al, 2004], various formulations are currently used to target their distribution to tissues, and to facilitate uptake of siRNAs into the relevant cell type. One approach that has been used successfully in vivo, in animal models (including in rodents and nonhuman primates) and humans employs intravenous delivery of siRNA in lipid nanoparticle (LNP) formulations [Soutschek et al, 2004; Morrissey et al, 2005; Geisbert et al, 2006; Judge et al, 2006; Zimmermann et al, 2006; Coelho et al, 2013; Tabernero et al, 2013]. Another approach for liver-specific gene silencing is subcutaneously administered siRNA conjugated to a N-acetylgalactosamine (GalNAc) carbohydrate ligand [Ashwell and Morell, 1974]. Conjugation of a triantennary GalNAc ligand to an siRNA enables hepatocyte binding and subsequent cellular uptake via the asialoglycoprotein receptor, resulting in engagement of the RNAi pathway and down regulation of hepatic proteins. Single and multiple doses of subcutaneously administered siRNA-GalNAc conjugates have been used to target transthyretin (TTR) mRNA for the treatment of TTR-mediated amyloidosis. ALN-TTRCSC has been found to be generally safe and well tolerated in Phase I and Phase II clinical trials in over 40 healthy volunteers and 18 subjects with familial amyloidotic cardiomyopathy and senile systemic amyloidosis [ALN-TTRSC-001; EudraCT 2012-004203-12; and ALN-TTRSC-002; EudraCT 2013-002856-33].

# 1.2. Inclisiran, an siRNA Therapeutic for Hypercholesterolemia

Inclisiran sodium is a chemically synthesized small interfering RNA (siRNA) double-stranded oligonucleotide, covalently linked to a ligand containing three Nacetylgalactosamine (GalNAc) residues.

Inclisiran is a long-acting, subcutaneously delivered, synthetic siRNA directed against PCSK9 that is conjugated to triantennary GalNAc carbohydrates. These carbohydrates bind to abundant liver-expressed asialoglycoprotein receptor (ASGPR), leading to inclisiran uptake specifically into hepatocytes.

When introduced into the hepatocyte, inclisiran engages the natural pathway of RNAi by binding intracellularly to the RNA-induced silencing complex (RISC), enabling it to cleave

messenger RNA (mRNA) molecules encoding PCSK9 specifically. The cleaved PCSK9 mRNA is degraded and thus unavailable for protein translation, which results in decreased levels of the PCSK9 protein. A single siRNA-bound RISC is catalytic and cleaves many transcripts and the duration of action is anticipated to be longer than other mechanisms.

#### 1.2.2. Clinical Studies

# 1.2.2.1. Clinical pharmacology

Inclisiran is inactive in plasma and acts directly in the hepatocytes leading to inhibition of PCSK9 protein synthesis. After SC administration of inclisiran, peak plasma concentrations were observed by 4 hours and became undetectable in plasma in 24 to 48 hours with a fast elimination half-life ( $t_{1/2}$ ) of 7.3 hours and dose-proportional increase in exposure parameters of maximum plasma concentration ( $C_{max}$ ) and area under the curve (AUC). There was no accumulation of inclisiran plasma concentrations following multiple weekly, biweekly or monthly dosing. Mean fraction excreted unchanged in the urine was around 25%. In vitro

studies using hepatic P450 metabolic enzymes showed that inclisiran neither inhibited nor induced common hepatic metabolic pathways.

Additional clinical pharmacology studies are ongoing or planned.

#### **1.2.2.2.** Clinical

Inclisiran has been studied in one completed Phase I (ALN-PCSSC-001) study (N=69) and one Phase II (ORION-1) study (N=501); dosing has completed in ORION-1 and the extended follow-up is ongoing.

ALN-PCSSC-001: Doses up to 800 mg as a single dose and two doses or more doses up to 500 mg were administered.

ORION-1: Up to 500 mg as a single dose on Day 1 or two doses on Day 1 and Day 90 (100 mg, 200 mg or 300 mg) were administered.

The efficacy data generated in these two studies show robust and prolonged reductions in PCSK9 and LDL-C levels in plasma. PCSK9 was reduced from baseline by around 75%. Mean LDL-C was reduced by around 50% with one dose of 300 mg and 55% with two doses of 300 mg given 30 or 90 days apart in both the Phase I and the ORION-1 study, respectively. This effect is still significant 210 days after a single dose and remains at around a mean of 50% when measured 120 days after the second dose given at Day 90 in the ORION-1 study. Other lipids and lipoproteins are also modified as would be expected from a drug acting on PCSK9 with a potentially beneficial modification of the overall atherogenic lipid profile [Ray et al, 2017].

To date, no clinically relevant safety concerns have arisen in these studies of inclisiran; collection and analysis of data up to Day 360 is ongoing in the ORION-1 (Phase II) study.

Based on these efficacy and safety data, 300 mg has been selected as the dose for subsequent clinical studies with a dosing at Day 1, Day 90, and every 6 months subsequently.

#### Safety:

In the ongoing Phase II (ORION-1) study with a follow up of more than 210 days, single doses of up to 500 mg on Day 1 or two doses (100 mg, 200 mg or 300 mg) (given 90 days apart) were also generally well tolerated and the majority of adverse events (AEs) in inclisiran-treated subjects with ASCVD and ASCVD risk equivalents were mild or moderate in intensity. Injection site reactions have been reported in around 5% of subjects receiving either one or two doses of inclisiran [Ray et al, 2017]. The emerging safety profile will be further evaluated in the ongoing Phase II (ORION 1) study and the subsequent planned studies.

#### **Efficacy:**

In the ongoing Phase II (ORION-1) study, in all single dose groups, maximal LDL-C reduction was observed between Day 30 and Day 60. At Day 30 the mean LDL-C reduction

from baseline was approximately 45% to 55% and at Day 60 was 44% to 51% in a dose dependent fashion with doses of 200 mg, 300 mg and 500 mg. Mean LDL-C remained significantly reduced from baseline over the course of the study in all inclisiran groups to Day 210.

In all groups, maximal reduction is PCSK9 levels was observed at Day 30 and the mean reduction from baseline was 66%, 71% and 74% in the 200 mg, 300 mg and 500 mg groups respectively.

In all double dose groups, maximal LDL-C reduction was observed after the second dose given at Day 90. At Day 120 the mean LDL-C reduction from baseline was 41% to 55% in a dose dependent fashion with doses of 100 mg, 200 mg and 300 mg.

At Day 180, the mean LDL-C reduction was between 35% and 53% in a dose dependent fashion across the dose range.

For subjects treated on Day 1 and Day 90, maximal reduction in PCSK9 levels was observed at Day 120 and the mean reduction from baseline was 60%, 73% and 75% with the 100 mg, 200 mg and 300 mg dose groups respectively. PCSK9 levels remained significantly reduced compared to baseline over the course of the study to Day 210 in all groups.

#### 1.3. Known and Potential Risks and Benefits

Subjects taking part in this clinical study will receive guideline recommended standard of care as background therapy (including maximally-tolerated statin therapy and/or other LDL-C lowering therapies) when administered inclisiran or placebo. Reduction of LDL-C has been associated with reduced CV risk both by epidemiology and in controlled clinical trials. Injection site reaction is the only event known to be attributed to inclisiran treatment. The safety profile of inclisiran observed to date is considered acceptable for this clinical trial.

An expanded risk-benefit summary is provided in the IB [Investigator Brochure, 2017].

# 1.4. Study Rationale

#### 1.4.1. Study Rationale

The overall safety data from inclisiran in nonclinical studies and clinical data from the Phase I and Phase II study (ORION-1), and multiple PCSK9 antibody studies demonstrated that potent lowering of PCSK9 is well tolerated in human subjects and support the dose and dosing schedule proposed in this Phase III study.

#### 1.4.2. Dose Rationale

Previous studies have shown that a 300 mg dose of inclisiran sodium is well tolerated and provides maximum efficacy (ie, doses higher than 300 mg did not provide additional efficacy in LDL-C lowering). The 300 mg dose of inclisiran will be administered on Day 1, Day 90, Day 270 and Day 450. Modelling and simulation has demonstrated that this regimen will allow for the necessary robust and sustained reduction in PCSK9 (and LDL-C) and has the potential to tackle the lack of adherence generally seen in the chronic management of

subjects with hypercholesterolemia. The 300 mg dose of inclisiran will be used for the entire duration of this study for subjects receiving inclisiran.

# 1.5. Study Population

This study will include male or female subjects ≥18 years of age with a history of ASCVD (CHD, CVD or PAD) or ASCVD-risk equivalents (type 2 diabetes, familial hypercholesterolemia, 20% or greater risk of a CV event as assessed by Framingham risk score or equivalent) and elevated LDL-C.

#### 2. STUDY OBJECTIVES AND PURPOSE

# 2.1. Primary Objective

The primary objective of this study is to evaluate the effect of inclisiran treatment on:

- LDL-C levels at Day 510
- Time adjusted percent change in LDL-C levels from baseline after Day 90 and up to Day 540 levels

# 2.2. Secondary Objectives

The secondary objectives of this study are to evaluate the effect of inclisiran on:

- PCSK9, total cholesterol, ApoB and non-HDL-C at Day 510
- LDL-C and PCSK9 levels over time to Day 540
- Mean maximum reduction in LDL-C levels
- LDL-C and PCSK9 levels over time in individual subjects
- Other lipids, lipoproteins, apolipoproteins
- Proportion of subjects achieving prespecified LDL-C targets
- Safety and tolerability profile of inclisiran

# 2.3. Exploratory Objectives

The exploratory objectives of this study are to collect/evaluate the effect of inclisiran on the following:

• CV events such as CV death, resuscitated cardiac arrest, non-fatal MI, and non-fatal stroke (ischemic and hemorrhagic)

#### 3. STUDY DESIGN

# 3.1. Type/Design of Study

[figure not shown]
This study will be a Phase III, placebo-controlled, double-blind, randomized trial in 1500 subjects with ASCVD (CHD, CVD or PAD) or ASCVD-risk equivalents (eg, type 2 diabetes and familial hypercholesterolemia, 20% or greater risk of a CV event as assessed by Framingham risk score or equivalent) and elevated LDL-C despite maximum tolerated dose of LDL-C lowering therapies to evaluate the efficacy, safety, and tolerability of inclisiran injection(s). The study will be a multicenter, international study (non-United States [US]). Informed consent will be obtained from subjects before the initiation of any study-specific procedures.

Subjects will be screened and approximately 1500 eligible subjects will be randomized: 750 subjects will be randomized to inclisiran sodium 300 mg and 750 subjects to placebo. Treatment allocation will be stratified by country and by current use of statins or other lipid-modifying therapies. Enrollment of statin intolerant subjects will be capped at 15% of total study enrollment. Each subject will receive an injection on Day 1 of blinded inclisiran or placebo, a second injection on Day 90 and subsequent injections on Day 270 and Day 450.

Subjects who have completed the study to Day 540 will be given the opportunity to enroll in a separate long-term extension study to collect long-term efficacy and safety data.

# 3.2. Schematic Diagram of Study Design

Figure 1: Schematic Diagram of Study Design

FUP=follow-up; V=visit

# 3.3. Primary Endpoints

The primary endpoints of this study are:

- Percentage change in LDL-C from baseline to Day 510
- Time adjusted percentage change in LDL-C from baseline after Day 90 and up to Day 540. This is the average percentage change in LDL-C from baseline over the period after Day 90 and up to Day 540.

# 3.4. Secondary Endpoints

The key secondary endpoints of this study are:

- Absolute change in LDL-C from baseline to Day 510
- Time adjusted absolute change in LDL-C from baseline after Day 90 and up to Day 540
- Percentage change from baseline to Day 510 in PCSK9, total cholesterol, ApoB, and non-HDL-C

The other secondary endpoints of this study are:

- Mean maximum percentage change in LDL-C
- Absolute change from baseline to Day 510 in PCSK9, total cholesterol, ApoB and non-HDL-C
- Absolute change and percentage change in LDL-C from baseline to each assessment time up to Day 540
- Individual responsiveness defined as the number of subjects reaching on treatment LDL-C levels of <25 mg/dL, <50 mg/dL, <70 mg/dL, and <100 mg/dL at Day 510
- Proportion of subjects in each group with greater or equal to 50% LDL-C reduction from baseline
- Absolute change and percentage change in other lipids, lipoproteins, apolipoproteins, and PCSK9 from baseline at each subsequent visit to Day 540
- Proportion of subjects in each group who attain global lipid targets for their level of ASCVD risk
- Safety and tolerability profile of inclisiran as measured by AEs, SAEs, vital signs, clinical laboratory values, ECG measurements and formation of ADA and subsequent characterization of ADA

# 3.5. Exploratory Endpoints

The exploratory endpoints of this study are:

• Incidence of CV death, resuscitated cardiac arrest, non-fatal MI, and non-fatal stroke (ischemic and hemorrhagic)

#### 3.6. Measures to Minimize/Avoid Bias

### 3.6.1. Blinded Study

This study will employ double-blind technique with a placebo control. Randomization via automated interactive response technology (IRT) will be used to assign subject to blinded investigational product kits. In addition, investigational product will be dispensed and administered in a blinded syringe. Blinding will minimize bias based on subject selection, baseline characteristics, clinical endpoint and AE reporting. Specifics on how the blind for the investigational product is maintained are provided in Section 5.5.

#### 4. SUBJECT POPULATION

This will be a multicenter, international study (non-US) in subjects with ASCVD (CHD, CVD or PAD) or ASCVD-risk equivalents (eg, type 2 diabetes and familial hypercholesterolemia, 20% or greater risk of a CV event as assessed by Framingham risk score or equivalent) and elevated LDL-C despite maximum tolerated dose of LDL-C lowering therapies.

# 4.1. Number of Subjects

Approximately 1500 subjects (at least 1425 evaluable) will be randomized.

#### 4.2. Inclusion Criteria

Subjects may be included in the study if they meet all of the following criteria:

- 1. Male or female subjects ≥18 years of age.
- 2. History of ASCVD (CHD, CVD or PAD; see APPENDIX A) or ASCVD-risk equivalents (type 2 diabetes, familial hypercholesterolemia, and including subjects whose 10-year risk of a CV event assessed by Framingham Risk Score or equivalent has a target LDL-C of <100 mg/dL).
- 3. Serum LDL-C≥1.8 mmol/L (≥70 mg/dL) for ASCVD subjects or ≥2.6 mmol/L (≥100 mg/dL) for ASCVD-risk equivalent subjects at screening.
- 4. Fasting triglyceride <4.52 mmol/L (<400 mg/dL) at screening.
- 5. Calculated glomerular filtration rate >30 mL/min by estimated glomerular filtration rate (eGFR) using standardized clinical methodology.
- 6. Subjects on statins should be receiving a maximally tolerated dose. Maximum tolerated dose is defined as the maximum dose of statin that can be taken on a regular basis without intolerable adverse events. Intolerance to any dose of any statin must be documented as historical AEs attributed to the statin in question in the source documentation and on the Medical History page of the electronic case report form (eCRF) (see APPENDIX B).
- 7. Subjects not receiving statin must have documented evidence of intolerance to all doses of at least two different statins (see APPENDIX B).
- 8. Subjects on lipid-lower therapies (such as a statin and/or ezetimibe) should be on a stable dose for ≥30 days before screening with no planned medication or dose change during study participation.
- 9. Subjects must be willing and able to give informed consent before initiation of any study-related procedures and willing to comply with all required study procedures.

#### 4.3. Exclusion Criteria

Subjects will be excluded from the study if any of the following exclusion criteria apply prior to randomization:

- 1. Any uncontrolled or serious disease, or any medical or surgical condition, that may either interfere with participation in the clinical study, and/or put the subject at significant risk (according to investigator's [or delegate] judgment) if he/she participates in the clinical study.
- 2. An underlying known disease, or surgical, physical, or medical condition that, in the opinion of the investigator (or delegate) might interfere with interpretation of the clinical study results.
- 3. New York Heart Association (NYHA) class IV heart failure or last known left ventricular ejection fraction <25%.
- 4. Cardiac arrhythmia within 3 months prior to randomization that is not controlled by medication or via ablation.
- 5. Major adverse cardiovascular event within 3 months prior to randomization.
- 6. Uncontrolled severe hypertension: systolic blood pressure >180 mmHg or diastolic blood pressure >110 mmHg prior to randomization despite anti-hypertensive therapy.
- 7. Active liver disease defined as any known current infectious, neoplastic, or metabolic pathology of the liver or unexplained elevations in ALT, aspartate aminotransferase (AST), >3x the ULN, or total bilirubin >2x ULN at screening confirmed by a repeat abnormal measurement at least 1 week apart.
- 8. Severe concomitant noncardiovascular disease that carries the risk of reducing life expectancy to less than 2 years.
- 9. History of malignancy that required surgery (excluding local and wide-local excision), radiation therapy and/or systemic therapy during the three years prior to randomization.
- 10. Females who are pregnant or nursing, or who are of childbearing potential and unwilling to use at least two methods of highly effective contraception (failure rate less than 1% per year) (eg combined oral contraceptives, barrier methods, approved contraceptive implant, long- term injectable contraception, or intrauterine device) for the entire duration of the study. Exemptions from this criterion:
  - a. Women >2 years postmenopausal (defined as 1 year or longer since last menstrual period) AND more than 55 years of age.
  - b. Postmenopausal women (as defined above) and less than 55 years of age with a negative pregnancy test within 24 hours of randomization.
  - c. Women who are surgically sterilized at least 3 months prior to enrollment.

- 11. Males who are unwilling to use an acceptable method of birth control during the entire study period (ie, condom with spermicide).
- 12. Known history of alcohol and/or drug abuse within the last 5 years.
- 13. Treatment with other investigational products or devices within 30 days or five half-lives of the screening visit, whichever is longer.
- 14. Planned use of other investigational products or devices during the course of the study.
- 15. Any condition that according to the investigator could interfere with the conduct of the study, such as but not limited to:
  - a. Subjects who are unable to communicate or to cooperate with the investigator.
  - b. Unable to understand the protocol requirements, instructions and study-related restrictions, the nature, scope, and possible consequences of the study (including subjects whose cooperation is doubtful due to drug abuse or alcohol dependency).
  - c. Unlikely to comply with the protocol requirements, instructions, and study-related restrictions (eg, uncooperative attitude, inability to return for follow-up visits, and improbability of completing the study).
  - d. Have any medical or surgical condition, which in the opinion of the investigator would put the subject at increased risk from participating in the study.
  - e. Persons directly involved in the conduct of the study.
- 16. Treatment (within 90 days of screening) with monoclonal antibodies directed towards PCSK9.

Subjects excluded for any of the above reasons may not be re-screened for participation at any time even if the exclusion characteristic has changed.

#### 4.4. Withdrawal Criteria

All subjects have the right to withdraw from the study at any point during treatment without prejudice. The investigator can discontinue any subject at any time if medically necessary. It will be documented whether or not each subject completed the clinical study. If study treatment or observations were discontinued, the reason will be recorded and the Sponsor should be notified promptly. The reasons a subject may discontinue their participation in the study could be from one of the following:

- AE
- Death
- Subject withdrew consent
- Physician decision
- Lost to follow-up
- Initiation of protocol-prohibited lipid-lowering therapy (eg, an approved PCSK9 inhibitor)

The applicable reasons above will be recorded in the eCRF. It is imperative to obtain complete follow-up data for all subjects whether or not they receive their assigned treatment or have discontinued investigational product. All data collected up until the time of subject withdrawal is to be entered into the eCRF. In addition, every attempt should be made to collect follow-up information except for those subjects who specifically withdraw consent release of such information. All procedures and laboratory specimens or tests requested for evaluation following administration of the investigational product should be carried out when possible whether or not a subject continues to receive treatment according the protocol. The attempts and any reason(s) for missing data as a result of the withdrawal will be captured in the source.

Participating study sites will be trained on the importance of completing study follow-up procedures and collecting the documentation required for missing data values. Any withdrawn subjects will not be replaced in this study.

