#### 4.4.1. Withdrawal from Study Medication

In the event a subject withdraws or is withdrawn from the study medication (eg, receives first injection and not second injection), the investigator will inform the Medical Monitor and the Sponsor immediately. If there is a medical reason for withdrawal, the subject will remain under the supervision of the investigator for protocol-specified safety follow up procedures. The IDMC will be notified.

It is imperative to obtain complete follow-up data (through Day 540 procedures) for all randomized subjects whether or not they receive their assigned treatment or have discontinued investigational product.

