#### 12.3. Protocol Deviations

This study will be conducted as described in this protocol, except for an emergency situation in which the protection, safety, and well-being of the subject requires immediate intervention, based on the judgment of the investigator (or a responsible, appropriately trained professional designated by the investigator). In the event of a significant deviation from the protocol due to an emergency, accident, or mistake, the investigator or designee must contact the Sponsor, or their agent, at the earliest possible time by telephone. This will allow an early joint decision regarding the subject's continuation in the study. The investigator and the Sponsor will document this decision. The IRB/EC will be informed of all protocol changes by the investigator in accordance with the IRB/EC established procedure. No deviations from the protocol of any type will be made without complying with all the IRB/EC established procedures.

In an effort to minimize deviations and missing data, the investigator and pertinent study staff will be trained on the operational aspects of implementing the study protocol and all required procedure by the sponsor/sponsor representatives. These trainings occur either as part of an Investigator Meeting or Site Initiation Visit. Retraining will occur at subsequent interim site monitoring visits as needed.

The following Protocol Deviations will require additional information in the eCRF explaining why the deviation occurred and what will be done to prevent it from re-occurring:

- Inclusion criteria violation
- Exclusion criteria violation
- Laboratory assessments not drawn at Day 1, Day 510 or Day 540 (EOS) visits
- Mis-Dosing for any reason other than subject safety or withdrawal (defined as missing dose or a dose delayed by more than 30 days)\*
- Subject taking any prohibited concomitant medication
- Change in baseline statin or other lipid-lowering therapy dose
- SAEs not reported to MDCO within 24 hours
- Informed Consent not signed prior to study entry

\*If the mis-dosing was unintended, ie, a medication error, the error should be reported as per instructions in Section 8.4.3.1, Medication Errors.

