6.3.4. Missing data handling

6.3.4.1 Efficacy

The sponsor will diligently follow up with each subject during the study through Day 540 \pm 14 days on all efficacy laboratory assessments of lipids/lipoproteins/biomarkers to keep missing data to a minimum regardless of whether the subject is on study treatment, uses ancillary therapies, experiences an adverse event, or adheres to the protocol (these data points are referred to as retrieved data). However, if missing data, defined as data not available from either scheduled (within the protocol defined visit window) or unscheduled visits, occurs for the primary or any of key secondary efficacy endpoints then that data will be imputed.

The primary method to impute missing data for the first co-primary efficacy endpoint (percentage change in LDL-C from baseline to Day 510) will be a multiple imputation washout model. The washout model will be performed on actual values, change and percentage change values are calculated after the imputation. All retrieved data for subjects who dropped out from study treatment are considered as non-missing data and will be utilized in all analyses. See [Appendix 2](#) for full details of the multiple imputation washout model.

In addition, sensitivity analyses using MMRM without multiple imputation and a control-based pattern mixture model (PMM, see details in [Appendix 3](#)) will be performed on the co-primary and key secondary efficacy endpoints to assess the impact of missing values. Note that the control-based PMM will be the primary method for imputing data for the second co-primary efficacy endpoint (time adjusted percentage change in LDL-C from baseline after Day 90 and up to Day 540).

Unless otherwise specified, missing data for all parameters not listed in the primary and key secondary endpoints will not be imputed and will be excluded from the associated analysis.

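### Protocol 4.4 lets the start of a prohibited lipid-lowering drug be recorded as leaving the study, so LDL-C that the SAP means to retrieve may never be collected

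*Protocol*

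**What the plan says.** Protocol 4.4 introduces its list with "The reasons a subject may discontinue their participation in the study could be from one of the following". The list includes death, withdrawn consent and loss to follow-up, and also "Initiation of protocol-prohibited lipid-lowering therapy (eg, an approved PCSK9 inhibitor". The applicable reason goes into the eCRF.

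The same section then says: "It is imperative to obtain complete follow-up data for all subjects whether or not they receive their assigned treatment or have discontinued investigational product". It adds that "every attempt should be made to collect follow-up information except for those subjects who specifically withdraw consent release of such information". Protocol 4.4.1, on withdrawal from study medication, says: "It is imperative to obtain complete follow-up data (through Day 540 procedures) for all randomized subjects".

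Protocol 12.3 lists "Subject taking any prohibited concomitant medication" as a deviation that needs an explanation in the eCRF.

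SAP 6.3.4.1 plans LDL-C follow-up to Day 540 "regardless of whether the subject is on study treatment, uses ancillary therapies, experiences an adverse event, or adheres to the protocol". It imputes only "missing data, defined as data not available from either scheduled (within the protocol defined visit window) or unscheduled visits". Its sentence on retrieved data names subjects who dropped out of study treatment. SAP 6.4.6.1 and Appendices 2 and 3 attach placebo-based imputation to subjects who discontinued the study.

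**The concern.** No passage says whether starting a prohibited lipid-lowering drug ends study treatment, study participation or neither. Protocol 4.4 puts it on a list of reasons for leaving the study. The follow-up rules and the SAP's retrieved-data rule are written mainly around subjects who leave treatment. A site can therefore record the event as the end of participation and stop drawing LDL-C, while another site keeps the subject in follow-up. The first subject's later values are imputed and the second subject's are observed.

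Such a loss would be related to outcome. Subjects enter with elevated LDL-C on maximally tolerated therapy, and those whose LDL-C stays high are the likelier candidates for an added drug. Placebo is saline, so more of them can be expected on placebo, although the documents give no figures by arm. The blinding sections (Protocol 3.6.1 and 5.5) deal with kits, vials and syringes and do not say whether post-baseline lipid results are withheld from sites. At stake are the size and meaning of the co-primary estimates, because the SAP intends to use LDL-C as measured whatever other therapy is taken.

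**Working it through.** **The plan's own figures.** 1500 × 0.95 = 1425 evaluable, as stated, or about 712 per arm. For a difference of 30 with SD 20 at one-sided 0.025, power is above 0.9999, so the stated figure of more than 90% holds. None of these figures depends on the withdrawal list.

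**What happens to a subject who starts a prohibited drug.**
- Followed up: the value is available, so it is not missing under SAP 6.3.4.1 and is analysed as observed.
- Closed out, placebo arm: Appendices 2 and 3 impute later values from placebo data (under missing at random in Appendix 2).
- Closed out, inclisiran arm: Appendix 2 imputes Day 510 from placebo Day 510 data, baseline and background therapy. Appendix 3 also uses placebo data.

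**Inputs for the size.** The documents give no rate of such use and no effect for it, so all of these are assumptions:
- q and r: share of placebo and inclisiran subjects who start such a drug and have no Day 510 value.
- m: fall in LDL-C in a placebo starter if followed, 20 to 50 points. The upper value borrows the roughly 50% that Protocol 1.2.2.2 reports for one 300 mg inclisiran dose.
- D: inclisiran effect, 30 points (Protocol 10.1) to 50 points (Protocol 1.2.2.2).
- A followed inclisiran starter falls by the larger of D and m.
- An imputed value represents about 0 change in either arm.

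**Formula** (inclisiran minus placebo, in percentage points):
- Followed: −(1−r)D − r·max(D, m) + q·m
- Lost and imputed: −(1−r)D
- Imputed minus followed: r·max(D, m) − q·m

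A negative result means a larger apparent benefit.

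| q | r | D=30, m=20 | D=30, m=50 | D=50, m=20 | D=50, m=50 |
|---|---|---|---|---|---|
| 1% | 0 | −0.2 | −0.5 | −0.2 | −0.5 |
| 3% | 1% | −0.3 | −1.0 | −0.1 | −1.0 |
| 5% | 0 | −1.0 | −2.5 | −1.0 | −2.5 |
| 5% | 1% | −0.7 | −2.0 | −0.5 | −2.0 |
| 5% | 5% | +0.5 | 0.0 | +1.5 | 0.0 |

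Example: q = 5%, r = 1%, D = 30, m = 50 gives 0.01 × 50 − 0.05 × 50 = −2.0.

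The shift is zero when r/q = m/max(D, m). That ratio is 0.4 for m = 20 and D = 50, and 1 for m = 50, so the direction depends on the ratio of starters between arms. If only a fraction of starters is lost, the same in both arms, the shift shrinks in proportion. For the time-adjusted endpoint only visits after the start are affected, so under the same assumptions the shift is no larger.

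**Scale.** SE = SD × √(2/712) = SD × 0.053. The documents give no SD on the percent scale. An assumed SD of 20 to 30 points gives an SE of 1.1 to 1.6 points.

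**Test result.** The smallest followed-up difference in the table is 30 − 0.05 × 50 = 27.5 points (q = 5%, r = 0). Even with an SD of 60 points, SE = 3.18 and 27.5/3.18 = 8.6. The conclusion on superiority would not change.

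**The case against.** The strongest reply is that the plan already asks for the data. The list in Protocol 4.4 is permissive, and the same section calls complete follow-up imperative, with withdrawn consent as the only stated exception. Protocol 4.5.1 asks subjects who stop study medication for good to complete the remaining visits. Footnote 1 to Table 2 provides an early EOS visit for those who stop treatment and decline further visits, and that visit still includes a lipid profile. A reason code, a deviation record and an analysis rule can all apply to one subject without contradiction. Tipping-point analyses are planned for both co-primary endpoints.

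Most of this stands, and it rules out several stronger readings that a reader might infer:
- That observed LDL-C is replaced by imputation. It is not: SAP 6.3.4.1 imputes only values that are unavailable from any visit.
- That Protocol 4.4 obliges a site to end follow-up. It does not.
- That placebo starters drop out of the analysis. The ITT population keeps every randomized subject.
- That the effect must be overstated. With equal rates in both arms the shift is zero or in the other direction.

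What remains is narrower. Protocol 4.4 lists the event as a reason to leave the study, yet does not make it an exception to follow-up. The SAP's retrieved-data sentence names dropout from treatment only. The tipping-point analyses test whether significance survives; they do not recover the estimate that would have come from measured values.

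**Conclusion.** The passages are inconsistent on one event, and the inconsistency can leave outcome-related gaps in LDL-C. If 1 to 5% of placebo subjects and no inclisiran subjects start a drug that lowers LDL-C by 20 to 50%, and all are lost, the Day 510 difference is enlarged by 0.2 to 2.5 points. If 1% on inclisiran do so against 3 to 5% on placebo, it is enlarged by 0.1 to 2.0 points. At 5% in each arm it moves 0 to 1.5 points towards a smaller effect.

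The upper values are comparable with or above the assumed SE, but they need every starter to be lost, which the follow-up rules are meant to prevent. The rates, the drug effect and the zero-change imputation are assumptions. The matter affects what is estimated and its size, not power or the test result. It is worth correcting because it is cheap and because values that are not collected cannot be recovered.

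**What to change.** Reconcile Protocol 4.4, 4.4.1 and 12.3 with SAP 6.3.4.1:
- Do not code the start of a prohibited lipid-lowering drug as the end of study participation. Record it as a concomitant medication and a deviation and, if the sponsor so decides, as a reason for stopping study treatment.
- State in Protocol 4.4 that LDL-C collection continues to Day 540 after this event unless consent is withdrawn.
- Extend the retrieved-data sentence in SAP 6.3.4.1 so that LDL-C collected after this event is analysed as observed, however disposition was recorded.

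Whether study drug continues after such a start is a clinical decision for the sponsor and lies outside this point.

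SAP 6.4.1 already tabulates discontinuation reasons by arm. Subjects already closed out for this reason can be counted there and put into the formula above in place of the assumed q and r.

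The cost is one protocol bullet, one SAP sentence, the eCRF disposition list and a site instruction. The estimated effect may come out slightly smaller.
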